Quetiapine	PGP substrates
Quinidine	PGP substrates
Ranitidine	PGP substrates
Ranolazine	PGP substrates
Rivaroxaban	PGP substrates
Rosuvastatin (acid)	PGP substrates
Saquinavir	PGP substrates
Selexipag	PGP substrates
Simeprevir	PGP substrates

PGP substrates: dose of these PGP substrates should be adjusted based on their respective labels	
Simvastatin (lactone)	PGP substrates
Sirolimus	PGP substrates
Sofosbuvir	PGP substrates
Sotrastaurin	PGP substrates
Tacrolimus	PGP substrates
Talinolol	PGP substrates
Tedisamil	PGP substrates
Teneligliptin	PGP substrates
Tenofovir	PGP substrates
Ticagrelor	PGP substrates
Velpatasvir	PGP substrates
Venetoclax	PGP substrates
Venlafaxine	PGP substrates
Verapamil	PGP substrates
Vinblastine	PGP substrates
Vincristine	PGP substrates
Voclosporin	PGP substrates
Ximelagatran	PGP substrates

UGT1A1 substrates: dose of these UGT1A1 substrates should be adjusted based on their respective labels	
Clopidogrel	UGT1A9 substrate
Furosemide	UGT1A9 substrate
Mycophenolic acid	UGT1A9 substrate
Probenecid	UGT1A9 substrate
Propofol	UGT1A9 substrate

17.1. Schedule of Assessments.....	42

This document is confidential.

1. Glossary of Abbreviations

Abbreviation	Description
ADR	Adverse Drug Reaction
AE	Adverse Event
AESI	Adverse Event of Special Interest
AIMS	Abnormal Involuntary Movement Scale
ATC	Anatomic Therapeutic Classification
BARS	Barnes Akathisia Rating Scale
BMI	Body Mass Index
C&A-GTS-QOL	Child and Adolescent Gilles De La Tourette Syndrome-Quality of Life Scale
CDRS-R	Children's Depression Rating Scale-Revised
CGI	Clinical Global Impression
CGI-TS-I	Clinical Global Impression Tourette's Syndrome of Improvement
CGI-TS-S	Clinical Global Impression Tourette's Syndrome of Severity
CTCAE	Common Toxicity Criteria for Adverse Events
DSMB	Data Safety Monitoring Board
ECG	Electrocardiogram
eCRF	Electronic Case Report Form
HbA1c	Hemoglobin A1c
HCl	Hydrochloride
ITT	Intention-to-Treat set
MedDRA	Medical Dictionary for Regulatory Activities
mitT	Modified Intent-to-treat
PARS	Pediatric Anxiety Rating Scale
PO	Oral (per os)
SAE	Serious Adverse Event
SAP	Statistical Analysis Plan
SD	Standard Deviation
SS	Safety Set
TEAE	Treatment Emergent Adverse Event
TS	Tourette's Syndrome

This document is confidential.

Statistical Analysis Plan for Interventional StudiesSponsor: Emalex Biosciences, Inc.; Protocol No.: EBS-101-OL-001

Abbreviation	Description
YGTSS-TTS	Yale Global Tic Severity Scale-Total Tic Score

This document is confidential.

2. Purpose

The purpose of this statistical analysis plan (SAP) is to ensure that the data listings, summary tables, and figures which will be produced, and the statistical methodologies that will be used, are complete and appropriate to allow valid conclusions regarding the study objectives.

2.1. Responsibilities

Syneos Health will perform the statistical analyses and are responsible for the production and quality control of all tables, figures, and listings.

2.2. Timings of Analyses

The primary analysis of safety and efficacy is planned after all subjects complete the final study visit or terminate early from the study.

This document is confidential.

3. Study Objectives

3.1. Primary Objective

The primary objective of this study is to evaluate the long-term safety and tolerability of ecopipam tablets in pediatric subjects (aged ≥ 6 to ≤ 18 years at Baseline of the EBS-101-CL-001 study) with Tourette's Syndrome (TS) that were previously enrolled in the EBS-101-CL-001 study (Phase 2b) and completed the Phase 2b study.

3.2. Secondary Objective(s)

The secondary objective of this study is to evaluate the durability of effect of ecopipam in pediatric subjects (aged ≥ 6 to ≤ 18 years at Baseline of the EBS-101-CL-001 study) with TS.

3.3. Brief Description

This is an international, multicenter, open-label, long-term extension study evaluating the safety of ecopipam tablets for the treatment of children and adolescent subjects with TS. Subjects who completed the Phase 2b, randomized double-blind efficacy and safety study (EBS-101-CL-001) and who continue to meet the inclusion/ exclusion criteria for this study will be eligible to participate in this study. All subjects will be titrated to a target dose of 2 mg/kg/day as subjects participating from previous studies will be tapered down from study medication to maintain the blind. Subjects will complete study visits every month for 1 year. Follow Up visits will be conducted 7 and 14 days after the last dose of study medication and a Follow Up phone call will be conducted 30 days after the last dose of study medication. Study Visits may be completed in locations other than clinic and/or safety and efficacy assessments required at these visits will be made available for remote administration due to restrictions as a consequence of the COVID-19 pandemic or other qualifying event.

Safety will be monitored throughout the study at all visits by repeated monitoring of adverse events (AEs), vital signs, the Columbia-Suicide Severity Rating Scale (C-SSRS), the Abnormal Involuntary Movement Scale (AIMS), the Barnes Akathisia Rating Scale (BARS), the Pediatric Anxiety Rating Scale (PARS) and Children's Depression Rating Scale-Revised (CDRS-R). In addition to these assessments, at Baseline, Months 1, 3, 6, 9 and 12 safety will also be monitored by clinical and laboratory evaluations, and electrocardiogram (ECG) monitoring. In addition to the scales aforementioned, the Yale Global Tic Severity Scale (YGTSS), Clinician Global Impression of Tourette Syndrome of Severity (CGI-TS-S), the Clinician Global Impression Tourette Syndrome of Improvement (CGI-TS-I) and the Gilles de la Tourette Syndrome—Quality of Life Scale for Children and Adolescents (C&A-GTS-QOL) will also be assessed at Baseline, Months 1, 3, 6, 9 and 12. At the Follow Up visits, AE monitoring, the C-SSRS, clinical and laboratory evaluations and vital signs will be assessed. A Follow Up phone call will be conducted 30 days after the last dose of study medication to assess AEs. Subjects will be monitored for signs of abuse, and withdrawal or dependence.

3.4. Subject Selection

3.4.1. Inclusion Criteria

Subjects eligible for inclusion in this study must fulfill all of the criteria listed in section 8.1 of the protocol.

3.4.2. Exclusion Criteria

Subjects will not be eligible if they meet any of the criteria listed in section 8.2 of the protocol.

This document is confidential.

3.5. Determination of Sample Size

This is a one-year safety and tolerability study as a follow up to the double-blind study (EBS-101-CL-001) and number of subjects enrolled in this is dependent on the number of subjects completing that study.

3.6. Treatment Assignment

Since this is an open-label study, all subjects that have cleared the inclusion/exclusion criteria will be administered ecopipam HCl at a target dose of 2 mg/kg/day.

3.7. Administration of Study Medication

Ecopipam Hydrochloride (HCl) will be supplied as 12.5-, 37.5-, 50-, 75-, and 100-mg tablets. The target dose is 2 mg/kg via oral (per os) (PO) administration.

During the 4-week titration period, the following ecopipam HCl doses will be administered for each of the weight bands:

- Those who weigh ≥ 18 - ≤ 23 kg will titrate from 12.5 mg daily to 37.5 mg daily: 12.5 mg during Week 1, 25 mg (two 12.5-mg tablets) during Week 2, and 37.5 mg during Weeks 3 and 4.
- Those who weigh >23 - ≤ 34 kg will titrate from 12.5 mg daily to 50 mg daily: 12.5 mg during Week 1, 25 mg (two 12.5-mg tablets) during Week 2, 37.5 mg during Week 3, and 50 mg during Week 4.
- Those who weigh >34 - ≤ 44 kg will titrate from 12.5 mg daily to 75 mg daily: 12.5 mg during Week 1, 25 mg (two 12.5-mg tablets) during Week 2, 50 mg during Week 3, and 75 mg during Week 4.
- Those who weigh >44 - ≤ 68 kg will titrate from 25 mg daily to 100 mg daily: 25 mg (two 12.5-mg tablets) during Week 1, 50 mg during Week 2, 75 mg during Week 3, and 100 mg during Week 4.
- Those who weigh >68 - ≤ 83 kg will titrate from 25 mg daily to 150 mg daily: 25 mg (two 12.5-mg tablets) during Week 1, 50 mg during Week 2, 100 mg during Week 3, and 150 mg (two 75-mg tablets) during Week 4.
- Those who weigh >83 kg will titrate from 25 mg daily to 200 mg daily: 25 mg (two 12.5-mg tablets) during Week 1, 50 mg during Week 2, 100 mg during Week 3, and 200 mg (two 100-mg tablets) during Week 4.

During the treatment phase, the following ecopipam HCl doses will be administered for each of the weight bands:

- Those who weigh ≥ 18 - ≤ 23 kg will receive 37.5 mg daily.
- Those who weigh >23 - ≤ 34 kg will receive 50 mg daily.
- Those who weigh >34 - ≤ 44 kg will receive 75 mg daily.
- Those who weigh >44 - ≤ 68 kg will receive 100 mg daily.
- Those who weigh >68 - ≤ 83 kg will receive 150 mg daily.
- Those who weigh >83 kg will receive 200 mg daily.

All doses will be administered PO once daily in the evening.

At the end of the open-label treatment phase, subjects will titrate off therapy and receive ecopipam HCl doses that will be reduced by 25 mg/day until off of drug; signs of symptoms of withdrawal will be monitored.

This document is confidential.

Subjects with weight changes during the course of the study resulting in change in weight band may titrate to the dosing of the new weight band at the discretion of the Investigator and with the approval of the Medical Monitor. If approved, the dose of study medication should be increased according to the titration scheme noted for the new weight band.

3.8. Study Procedures and Flowchart

Subjects will complete study visits every month for 1 year. Follow Up visits will be conducted 7 and 14 days after the last dose of study medication and a Follow Up phone call will be conducted 30 days after the last dose of study medication.

See Appendix section 16.1 for the Schedule of Assessments.

This document is confidential.

4. Endpoints

4.1. Efficacy Endpoints

- Changes in the Yale Global Tic Severity Scale – Total Tic Score (YGTSS-TTS) from baseline to Months 1, 3, 6, 9, 12.
- Changes in the Yale Global Tic Severity Scale – Impairment (YGTSS-I) and Global (YGTSS-TTS + YGTSS-I = YGTSS-GS) from baseline to Months 1, 3, 6, 9, 12.
- Changes in Clinical Global Impression of Tourette Syndrome of Severity (CGI-TS-S) from Baseline to Months 1, 3, 6, 9, 12.
- Clinician Global Impression Tourette Syndrome of Improvement (CGI-TS-I) at Months 1, 3, 6, 9, 12.
- Changes in Gilles de la Tourette Syndrome—Quality of Life Scale for Children and Adolescents (C&A-GTS-QOL) from Baseline to Months 1, 3, 6, 9, 12.

4.2. Safety Endpoints

- Assessment of AEs or serious adverse event (SAEs) and their relationship to study drug (Unrelated, Possible Related, or Probably Related).
- Changes from baseline in clinical laboratory analysis (Hematology, Chemistry, Urinalysis and Hemoglobin A1c (HbA1c) assessments).
- Changes from baseline in vital signs.
- Changes from baseline in ECG.
- Changes from baseline in physical examination findings.

4.3. Other Safety Endpoints

- Changes from baseline in Columbia Suicide Severity Rating Scale (C-SSRS) results.
- Changes from baseline in Abnormal Involuntary Movement Scale (AIMS) results.
- Changes from baseline in Barnes Akathisia Rating Scale (BARS) results.
- Changes from baseline in Children's Depression Rating Scale-Revised (CDRS-R) results.
- Changes from baseline in Pediatric Anxiety Rating Scale (PARS) results.

This document is confidential.

5. Analysis Sets

5.1. Enrolled Set

The Enrolled Set will include all subjects who complete the Phase 2b, randomized double-blind efficacy and safety study (EBS-101-CL-001) and who continued to meet the inclusion and exclusion criteria and enrolled in this study. The Enrolled Set will be used for subject listings and summaries of subject disposition.

5.2. Safety Set

The Safety Set (SS) will include all subjects who received at least one dose of study drug from the open labelled study. The Safety Population will be used for the analysis of the safety endpoints.

5.3. Modified Intent-to-Treat Set

The Modified Intention-to-Treat (mITT) set will consist of all subjects who receive at least one dose of study drug and have at least one post Baseline scoring of YGTSS. All efficacy analyses will be conducted using the mITT population.

5.4. Intention-to-Treat Set

The Intention-to-Treat (ITT) set will include all enrolled subjects. All efficacy analysis will also be conducted using the ITT population.

This document is confidential.

6. General Aspects for Statistical Analysis

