7.5. Criteria for Subject Study Discontinuation

A subject may elect to discontinue from the study at any time for safety or personal reasons. All subjects who discontinue from the study should complete the early study discontinuation procedures.

Any subject with a new positive response on questions 4 and/or 5 of the C-SSRS will be immediately discontinued and evaluated for risk. Dosing may be restarted at the discretion of the Investigator following consultation with the Sponsor or its designee.

Subjects who discontinue early from the study will be discontinued for one of these primary reasons: AE(s), lost to follow-up, subject choice, inadequate therapeutic effect, and administrative/other. In addition to the primary reason, the subject may have indicated 1 or more of these reasons as secondary reasons for discontinuation. Study disposition information will be collected on the case report form (CRF).

 Table 2:
 Study Design and Schedule of Assessments

Assessment ⁴	Baseline* (Titration)					Tr	eatmo	End of Study / Early Termination	Follow Up Visit	Follow Up Phone Call					
Study Month	0	1	2	3	4	5	6	7	8	9	10	11	12	One and Two Weeks Post Last Dose	30 Days After Last Dose
Study Visit Number	1	2	3	4	5	6	7	8	9	10	11	12	13	14 & 15	
Visit Window		±3 days	±3 days	±3	±3	±3 days	±3 days	±3 days	±3 days	±3 days	±3 days	±3 days	±3 _{days}	±3 _{days}	±3days
Informed Consent	X														
Inclusion/ Exclusion	X														
Medical/Psychiatric/ Medication History	X														
Physical Examination	X	X		X			X			X			X	X	
Vital Signs ¹	X	X	X	X	X	X	X	X	X	X	X	X	X	X	
ECG	X	X		X			X			X			X		
Laboratory Tests (Hematology, Chemistry and Urinalysis) ²	X	X		X			X			X			X	X	
Urine Drug Screen	X	X		X			X			X			X		
Urine Pregnancy Test	X	X		X			X			X			X		
HbA1c		X		X			X			X			X		
YGTSS Score	X	X		X			X			X			X		
CGI-TS-I		X		X			X			X			X		

Confidential Page 34 of 76

Assessment ⁴	Baseline* (Titration)					Tr	eatm	End of Study / Early Termination	Follow Up Visit	Follow Up Phone Call					
Study Month	0	1	2	3	4	5	6	7	8	9	10	11	12	One and Two Weeks Post Last Dose	30 Days After Last Dose
Study Visit Number	1	2	3	4	5	6	7	8	9	10	11	12	13	14 & 15	
CGI-TS-S	X	X		X			X			X			X		
C&A-GTS-QOL	X	X		X			X			X			X		
Columbia Suicide Severity Rating Scale	X	X	X	X	X	X	X	X	X	X	X	X	X	X	
Abnormal Involuntary Movement Scale (AIMS)	X	X	X	X	X	X	X	X	X	X	X	X	X		
Barnes Akathisia Ratings Scale (BARS)	X	X	X	X	X	X	X	X	X	X	X	X	X		

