6.2. Key Definitions

Treatment emergent adverse events (TEAEs) are defined as any adverse events that start or increase in intensity on or after the first dose of open-label treatment on Day 1.

Duration of exposure is defined as (Date of Last Dose – Date of First Dose) +1. If date of last dose is unknown, then the date of last clinical visit will be used to impute the date of last dose.

Baseline is defined as the last measurement taken before the first dose of open-label treatment on Day 1.

Change from baseline will be calculated for the post-baseline assessment as post-baseline value – baseline value.

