7.4.2. Concomitant Medication

Concomitant medications are defined as medication on the eCRF that are taken on or after or are ongoing at the start date of dosing. Concomitant medications will be summarized by ATC level 2 and preferred drug name for the Safety Set.

This document is confidential.

8. Efficacy

The mITT as well as ITT set will be used for the analysis of the efficacy endpoints.

The YGTSS, CGI-TS-S, and C&A-GTS-QOL will be assessed at Baseline, Months 1, 3, 6, 9 and 12. The CGI-TS-I will be assessed at Months 1, 3, 6, 9 and 12.

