8.1. Yale Global Tic Severity Scale (YGTSS)

The YGTSS is a clinician-completed rating scale used to quantify overall tic severity as well as specific subdomains of tic number, frequency, intensity, complexity and interference. Each of these subdomains is scored, on a 5-point scale, separately for motor and vocal tics and then summed across both motor and vocal tics to yield a total tic score (TTS) ranging from 0 to 50. The YGTSS also provides for an overall impairment rating (0 = “none” to 50 = “severe”). Global YGTSS (YGTSS-GS) is the total of YGTSS-TTS and impairment score (YGTSS-I). Efficacy will be analyzed for the YGTSS-TTS, YGTSS-I and YGTSS-GS.

The observed YGTSS-TTS along with motor and phonic subdomains, YGTSS-I and YGTSS-GS values and their changes from baseline will be summarized by visit. The paired t-test will be used for analyzing the change from baseline within treatment.

The percent of subjects with a 25% or greater improvement on the YGTSS-TTS score at any time between the Baseline visit and post-baseline visit will be considered as a Response. Any subject who has at least 1 Response (>=25% improvement) will be considered as a Responder; otherwise, the subject will be considered a Non-Responder. Responder and Non-Responder will be summarized at each post-baseline visit and overall.

YGTSS-TTS will also be summarized by treatment group (ecopipam, placebo and overall) from CL (EBS-101-CL-001) study.

All YGTSS data will be presented in a listing.

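### The ITT rerun adds no post-baseline YGTSS data to the mITT analysis, and no planned analysis addresses subjects missing from the late-visit means that describe durability

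*SAP*

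**What the plan says.** - **Analysis sets.** SAP 5.3 defines the mITT set as "all subjects who receive at least one dose of study drug and have at least one post Baseline scoring of YGTSS". SAP 5.4 then says "The Intention-to-Treat (ITT) set will include all enrolled subjects", and adds: "All efficacy analysis will also be conducted using the ITT population". Section 10 and the index of tables list ITT versions of the YGTSS-TTS, subscale, Global and Impairment tables (14.2.1.1.1b to 14.2.1.1.4b), and of the CGI-TS-S, CGI-TS-I and C&A-GTS-QOL tables.
- **Outcome and test.** SAP 6.2: "Change from baseline will be calculated for the post-baseline assessment as post-baseline value – baseline value". SAP Section 8: "The YGTSS, CGI-TS-S, and C&A-GTS-QOL will be assessed at Baseline, Months 1, 3, 6, 9 and 12". SAP 8.1: "The paired t-test will be used for analyzing the change from baseline within treatment". The same test applies to CGI-TS-S (8.2) and C&A-GTS-QOL (8.3).
- **Missing data.** SAP 6.3 covers partial dates only. The C&A-GTS-QOL rule in 8.3 fills a single missing item, not a missed visit. SAP 6.4 has a rule labelled modified LOCF: an early-termination (ET) visit is assigned to the next visit scheduled for that scale. It does not carry the score to any later visit.
- **Stopping.** Protocol 7.5 lists five primary reasons for early discontinuation: adverse events, loss to follow-up, subject choice, "inadequate therapeutic effect, and administrative/other". Protocol 8.3 has end-of-study procedures done at discontinuation only where possible.
- **Timing.** SAP Section 10 records that the ITT set, the ITT efficacy tables and the ET reassignment were added after database lock.

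**The concern.** Durability of effect is the secondary objective and there is no control arm, so the by-visit changes from baseline are the main evidence for it. If subjects who respond poorly leave more often, the mean among those remaining can hold steady or improve with no change in any individual. A reader who sees an mITT table and an ITT table agree will normally take that as reassurance about excluded subjects. For YGTSS, the agreement follows from the definitions and carries no such information.

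**Working it through.** **1. Who is in ITT but not in mITT?** Such a subject either was not dosed or has no post-baseline YGTSS. Without a post-baseline score there is no change under SAP 6.2. An undosed subject has no baseline either if SAP 6.2 is read literally, because baseline is defined relative to the first open-label dose. The extra subjects therefore contribute nothing to a YGTSS change summary or paired t-test.

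The rules were applied to simulated data with 100 enrolled, 5 without any post-baseline YGTSS, and 30% total dropout (all assumed):

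| | ITT | mITT |
|---|---|---|
| Set size | 100 | 95 |
| Baseline mean | 32.28 | 32.40 |
| n at Months 1, 3, 6, 9, 12 | 95, 95, 93, 86, 78 | 95, 95, 93, 86, 78 |

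The difference in mean change and in the paired t statistic was exactly 0 at every visit.

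**2. Who is in the Month 12 mean?** YGTSS is scheduled at Months 1, 3, 6, 9 and 12. Under SAP 6.4, an ET score counts at Month 12 if the latest scheduled visit was Month 9, 10 or 11. If it was earlier, the score falls at Month 9 or before and the subject is absent from Month 12. In the simulated data, the 78 at Month 12 were 70 completers plus 8 reassigned ET scores.

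As arithmetic, assume 100 enrolled, 5 with no post-baseline YGTSS, an ET visit for every other dropout, and latest visits spread evenly over Months 1–11, so that 3/11 reach Month 12. Completers change by −5.6 (the Day 30 ecopipam mean in the earlier paediatric crossover study, Protocol 5.2.2.1) and dropouts by 0. At 30% dropout:

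- ET scores at Month 12: (30 − 5) × 3/11 = 6.8, so n = 70 + 6.8 = 76.8
- Completer share: 70/76.8 = 91%
- Planned Month 12 mean: 70 × (−5.6)/76.8 = −5.10
- Mean over all enrolled with dropouts at zero: 70 × (−5.6)/100 = −3.92

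From 20% to 50% dropout, the completer share runs from 95% to 80%, the planned mean from −5.33 to −4.50, and the all-enrolled mean from −4.48 to −2.80.

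**3. How far could selection move the mean?** The documents give no sample size or dropout rate, so this is illustration only. Assumed inputs: n = 120, true Month 12 change −8, between-visit correlation 0.6, dropout depending on the current score (weakly to strongly), and every ET score collected and placed as in SAP 6.4. The SD of 8.7 is that of the same Day 30 change. There were 600 trials per scenario. Overstatement = (|mean| − 8)/8.

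| Dropout | Observed-case Month 12 result | Overstatement |
|---|---|---|
| 10% | bias −0.2 to −0.6 | about 2–7% |
| 20% | mean −8.4 to −9.1 | about 5–13% |
| 36% | mean −8.8 to −9.9 | about 10–24% |
| Unrelated to score | no bias | 0 |

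Rounding a mean to one decimal can shift a percentage by 0.05/8 = 0.6 points. A likelihood-based repeated-measures estimate on the same data gave −8.0 to −8.1 at 36% dropout and −8.0 at 20%. At 36% its standard error was similar to the observed-case one, about 0.9.

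That near-zero bias depends on the ET score being observed. With ET scores collected for half or none of the dropouts at 36% dropout, the model's bias was −0.3 to −1.3 points (0.3/8 = 4% to 1.3/8 = 16%), still smaller than the observed-case bias.

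**4. Does another planned output fill the gap?** The responder table (14.2.1.1.5) is mITT only. Overall responder status needs just one improvement of 25% or more at any time, so an early responder who leaves still counts. Percentages use subjects with an observation as the denominator (SAP 12.2.5.2). No mixed model or dropout sensitivity analysis is planned.

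**The case against.** The case on the other side has substance and limits the point in several ways.

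- A reader might infer that no ITT table can differ from its mITT counterpart. The documents do not support that. Header N and baseline rows can differ. Because mITT depends on YGTSS alone, CGI-TS-S, CGI-TS-I or C&A-GTS-QOL results can differ for a subject who has that scale but no post-baseline YGTSS.
- A reader might infer that Month 12 uses only subjects still in the study. SAP 6.4 says otherwise, as step 2 shows.
- No passage calls the ITT run a dropout check. The point is that it cannot serve as one, not that the SAP misdescribes it.
- A reader might take selection for response as established. Inadequate effect is one of five listed reasons, and the Protocol synopsis also ends treatment at NDA approval or if development stops, neither of which reflects a subject's response. The documents give no counts by reason.
- This is an uncontrolled safety extension with descriptive efficacy. Visit n, discontinuation reasons and YGTSS listings will be reported, so attrition will be visible. No model here separates drug effect from the natural decline in tics described in Protocol 5.1.

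All of this stands. It narrows the claim and its size, but it does not supply an analysis for subjects who leave before Month 9.

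**Conclusion.** The point holds in this limited form. For all four YGTSS outcomes, the ITT change results equal the mITT results by construction. The late-visit means come close to a completer analysis: completers are 80–95% of Month 12 under the step 2 assumptions. No planned analysis addresses subjects who left earlier. Late means may therefore overstate durability, but whether they do, and by how much, depends on dropout rate, timing and reasons that the documents do not give. The percentages in step 3 are conditional on their inputs and are not an estimate of bias in this trial. The matter should be corrected; it concerns the secondary objective and leaves the primary safety objective untouched.

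**What to change.** 1. Beside the observed-case tables, add an MMRM of change from baseline for YGTSS-TTS, YGTSS-GS and CGI-TS-S, with visit, baseline value and unstructured covariance, fitted to all observed scores. Report Month 3 to Month 12 means with 95% confidence intervals.
2. Add one sensitivity analysis that assigns zero change at later visits to subjects who stop for an adverse event or lack of effect. It is needed because the model keeps some bias when ET scores are missing.
3. Label both post hoc, since the database is locked.
4. Footnote ITT change tables 14.2.1.1.1b to 14.2.1.1.4b as adding no post-baseline data, or drop those tables only. Keep the CGI and C&A-GTS-QOL ITT tables.

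The cost is one model and one sensitivity table on data already collected. The downside is that the Month 12 estimate may look less favourable.
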